### **7.8.2 Laboratory data**

Only the date of samples are collected; laboratory data are not collected. Laboratory values that are considered clinically relevant will be recorded with Baseline Conditions or Adverse Events as appropriate.

### **7.8.3 Vital signs**

Only descriptive statistics are planned for this section of the report. A summary of the actual value and the change from baseline will be presented in 4-week periods for the following parameters: Systolic blood pressure, Diastolic blood pressure, Pulse rate, Temperature, Weight.

Other than at baseline, repeat, ad-hoc or unscheduled data will not be included in the summary tables.

A listing for pregnancy test results of patients with child bearing potential will be provided.

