Duration of treatment: Continuous treatment in the absence of progressive disease and trial withdrawal criteria specified in Section 3.3.4. In this trial, progression is determined by investigator. Afatinib must be permanently discontinued when investigator judges that patient is no longer benefiting from treatment with afatinib.			
Criteria for efficacy: Time to symptomatic progression (TTSP) as determined by investigator			
Criteria for safety: Adverse events according to Common Terminology Criteria (CTCAE Version 3)			
Statistical methods: Exploratory descriptive statistics of demographic, efficacy and safety data will be presented as appropriate.			

Proprietary confidential information.

© 2019 Boehringer Ingelheim International GmbH or one or more of its affiliated companies. All rights reserved.

This document may not - in full or in part - be passed on, reproduced, published or otherwise used without prior written permission.

FLOW CHART

Procedure	Screening		Baseline	Treatment and Safety evaluation		End of Treatment	Follow-up
	V1*			V2, V3, V4, V5, V6. Onwards	V4, V7, V10, V13, V16... Onwards		
Visits (V)	V1*			V2, V3, V4, V5, V6. Onwards	V4, V7, V10, V13, V16... Onwards	EOT**	FU#
Days	Day -1 (-28 to -1)	Day 1	Day 15 (±3) (phone call)	Day 28 (-7/+2 days) of every treatment cycle	Day 28 (-7/+2) of every 3rd treatment cycle	0-14 Days after last trial drug intake	EOT+ 28 (+7)
Informed consent ¹	X						
Demographics	X						
Medical history	X						
In/Exclusion criteria	X						
Physical examination ²	X			X		X	
Tumour clinical assessment ³	X				X	X	
ECOG	X			X		X	
Safety laboratory testing ⁵	X				X	X	
Urine examination ⁶	X					X	
Pregnancy test ⁷	X					X	
Adverse events	X	X	X ⁸	X		X	X ⁹
Dispense trial medication		X		X			
Compliance				X		X	
Termination of trial medication						X	
Patient Status							X
Diarrhoea diary completion ¹⁰		X		X ¹¹			

* Afatinib will be dispensed only after verification that all trial requirements are met.

1. Written informed consent must be obtained before any screening/baseline assessments are performed. All screening procedures conducted as per site standard of care prior to ICF and within the screening period of 28 days prior to first dose can be used for the study.
2. Includes vital signs (pulse, blood pressure), temperature, weight (kg) and an ECOG performance score. Height is only captured at screening visit only.

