4.1.4.1 Dose reduction scheme

Treatment related adverse events will be managed by treatment pauses and subsequent dose reductions of afatinib according to the schedule described in Table 4.1.4.1: 1. Dose reductions will apply to individual patients only. Once the dose has been reduced, it cannot be increased later.

Proprietary confidential information.

© 2019 Boehringer Ingelheim International GmbH or one or more of its affiliated companies. All rights reserved.

This document may not - in full or in part - be passed on, reproduced, published or otherwise used without prior written permission.

The investigator is responsible for determining the necessity and frequency of any additional/unscheduled visits as well as the extent of the evaluation (e.g., physical examination, laboratory testing, adverse events, etc.) performed at these visits. At a minimum the investigator should note in the patient's chart when an additional/unscheduled visit occurs and make relevant entries on the AE and medication dispensing eCRFs.

To prevent the development of more severe adverse events, treatment related diarrhoea, nausea and vomiting or rash should be managed early and proactively as described in [Appendix 10.1](#).

Table 4.1.4.1: 1 Dose reduction scheme

AE type and CTC-AE*Grade	Action	Dose Reduction Scheme
Events related to trial drug: 
 • Diarrhoea Grade 2 persisting for 2 or more consecutive days (48 hours) despite adequate anti-diarrhoeal medication/hydration • Reduced renal function to \geq Grade 2 as measured by serum creatinine, proteinuria or decrease in glomerular filtration rate of more than 50% from baseline • Any drug related AE Grade ≥ 3 	Pause treatment until patient has recovered to Grade ≤ 1 or baseline ¹ . Resume treatment at a reduced dose according to the Dose Reduction Column. If patient has not recovered to Grade ≤ 1 or baseline ¹ within 6 weeks trial treatment must be permanently discontinued ² .	Resume with dose reduction by 10mg decrements. If patient cannot tolerate 20mg/day, permanent discontinuation of afatinib should be considered.

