6.2.2 Treatment periods

Safety evaluation visits are to be conducted after the initiation of afatinib, at Day 28 (-7/+2)/Visit 2 and every 28 (-7/+2) days onwards. Additional safety evaluation visits may be conducted as necessary, at the investigator's discretion. The investigator is responsible for determining the necessity and frequency of the additional safety visits as well as the extent of the evaluation (physical examination, laboratory testing, etc.) at each visit.

Investigator must make a phone call to patient on day 15 to enquire about tolerability. If lack of tolerance is suspected, patient must visit site for dose reduction.

Proprietary confidential information.

© 2019 Boehringer Ingelheim International GmbH or one or more of its affiliated companies. All rights reserved.

This document may not - in full or in part - be passed on, reproduced, published or otherwise used without prior written permission.

Table 6.2.2:1 Visit 2/Day 28 (-7/+2) and every 28 (-7/+2) days onwards - treatment and safety evaluation

	The following must be performed and information recorded in the patient's chart	What to include in eCRF
Physical examination	Physical examination results (see Flow Chart).	Verify that this physical examination was performed and record results (see Flow Chart).
Tumour assessment	Tumour Assessment will be based on the assessment of cancer related symptoms and, if available, radiologic assessments as per standard of care at the site. There is no specific schedule for tumour assessment and can be according to standard of care or every 3 cycles.	Tumour assessment where available will be captured in the CRF
Safety Laboratory Testing	Hematology, and Biochemistry examination. See Section 5.2.3 for recommended safety laboratory evaluations and Flow Chart for schedule.	Verify if all recommended safety laboratory testing was performed and that values were acceptable according to the protocol. If not, see Sections: 4.1.4.1 and 5.2.2.1 No lab values are to be recorded on the eCRF.
Urine Examination – Optional	Urine examination. See Section 5.2.3 for recommended urine examinations. Urine Examination is optional at this visit and may be performed at the discretion of the investigator and in accordance to the current standard of care.	Verify if all recommended urine testing was performed. No values from the urine examination are to be recorded on the eCRF.

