7.3.3 Safety analyses

All treated patients will be included in the safety analysis. In general, safety analyses will be descriptive in nature and will be based on BI standards. No hypothesis testing is planned.

Statistical analysis and reporting of adverse events will concentrate on treatment-emergent adverse events. To this end, all adverse events occurring between first drug intakes until 28 days (inclusive) after last treatment administration will be considered 'treatment-emergent'. Adverse events that start before first drug intake and deteriorate under treatment will also be considered as 'treatment-emergent'.

Frequency, severity, and causal relationship of adverse events will be tabulated by system organ class and preferred term after coding according to the current version of the Medical Dictionary for Drug Regulatory Activities (MedDRA).

Adverse events will be graded according to CTCAE, Version 3.0 ([R04-0474](#)).

CTC grades will be applied to laboratory parameters using the current BI oncology standard as detailed in the document 'Conversion of laboratory parameters to CTCAE grades within BI.'

Vital signs, physical examinations, or other safety-relevant data observed at screening, baseline, during the course of the trial and at the end-of-trial evaluation will be assessed with regard to possible changes compared to findings before start of treatment.

Proprietary confidential information.

© 2019 Boehringer Ingelheim International GmbH or one or more of its affiliated companies. All rights reserved.

This document may not - in full or in part - be passed on, reproduced, published or otherwise used without prior written permission.

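### SAP 7.8.3 gives end-of-treatment values no stated place and plans no per-patient worst or last value, so its tables can understate weight and vital-sign change

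*SAP*

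**What the plan says.** - SAP 7.8.3 on the planned table: "A summary of the actual value and the change from baseline will be presented in 4-week periods for the following parameters", followed by systolic and diastolic pressure, pulse, temperature and weight. The section is descriptive: "Only descriptive statistics are planned for this section of the report".
- The same section on off-schedule values: "Other than at baseline, repeat, ad-hoc or unscheduled data will not be included in the summary tables". The only listing it plans is of pregnancy tests.
- SAP 6.7 uses nominal eCRF visits without windowing. No rule assigns EOT to a 4-week period.
- Protocol 7.3.3 says that vital signs and other safety data "observed at screening, baseline, during the course of the trial and at the end-of-trial evaluation will be assessed with regard to possible changes" from the findings before treatment.
- Flow Chart footnote 2 defines the physical examination: "Includes vital signs (pulse, blood pressure), temperature, weight (kg) and an ECOG performance score". The chart schedules it at screening, at each 28-day visit and at EOT, which falls 0 to 14 days after the last dose.
- Protocol 4.1.4.1 on visits outside the schedule: "The investigator is responsible for determining the necessity and frequency of any additional/unscheduled visits". Protocol 6.2.2, on the day-15 call: "If lack of tolerance is suspected, patient must visit site for dose reduction".

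**The concern.** Safety is the primary objective (Protocol 2.2). Laboratory values are not collected (SAP 7.8.2) and for ECGs only the date is collected (SAP 7.8.4), so weight and vital signs are among the few safety variables actually measured.

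The expected toxicity bears directly on them. Protocol 2.3 reports diarrhoea in nearly all patients, starting within 2 weeks. Protocol 1.2 lists stomatitis and decreased appetite among the common effects, and Appendix 10.1.1 warns of dehydration. The first scheduled on-treatment examination is at day 28 (-7/+2), that is day 21 to 30. A weight taken at an early low point is therefore likely to be off-schedule.

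Three features of the table then work in the same direction: off-schedule values are left out, EOT values have no defined row, and each row holds only patients still being seen. What is at stake is whether a reader of the report can tell how many treated patients had a material weight loss or pressure change.

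**Working it through.** The documents give no figure on this point and no formal sample size, so there is nothing to reproduce. The steps below compare the texts and then illustrate each mechanism separately.

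**1. The EOT gap.** Protocol 7.3.3 names an end-of-trial evaluation. EOT is the last visit with a scheduled physical examination, since the follow-up visit may be a phone call. SAP 7.8.3 has only 4-week rows, and SAP 6.7 rules out windowing. EOT values are scheduled, so the off-schedule rule does not remove them, but nothing says where they appear.

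**2. Scale from the cited trials, applied to about 500 patients (Protocol 2.3 and 3.3).** AEs leading to dose reduction: 500 × 0.322 = 161 (trial 1200.34) to 500 × 0.572 = 286 (trial 1200.32). AEs leading to discontinuation: 500 × 0.140 = 70 (trial 1200.32). The share handled at unscheduled visits is not given.

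**3. Shrinking rows.** Assume exponential time on treatment, S(t) = 0.5^(t/m), with the cited median PFS as stand-in: m = 11.0 months (1200.34) to 13.6 months (1200.32, common mutations). Months = weeks × 7/30.4375.

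| Week | m = 11.0 | m = 13.6 |
|---|---|---|
| 12 | 84% | 87% |
| 24 | 71% | 76% |
| 52 | 47% | 54% |

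**4. Attrition, assumed inputs.** Let 20% of patients lose weight linearly to 10% by month 2 and stop at a median of 3 months. The other 80% lose 1% and stop at a median of 13 months. The row mean is −(0.2·S₃·loss + 0.8·S₁₃·1)/(0.2·S₃ + 0.8·S₁₃), where S₃ and S₁₃ are S(t) with m = 3 and m = 13.

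| Week | 0.2·S₃ | Loss in that group | 0.8·S₁₃ | On treatment | Row mean |
|---|---|---|---|---|---|
| 4 | 0.162 | 4.6% | 0.762 | 92% | −1.6% |
| 8 | 0.131 | 9.2% | 0.725 | 86% | −2.25% |
| 12 | 0.106 | 10% | 0.690 | 80% | −2.2% |
| 24 | 0.056 | 10% | 0.596 | 65% | −1.8% |
| 48 | 0.016 | 10% | 0.444 | 46% | −1.3% |

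Patients ever losing at least 5% are those still on treatment at month 1: 0.2 × 0.5^(1/3) = 0.159, or 16%. With a share of 10% or 30%, the week-48 mean is −1.1% or −1.5%, and 8% or 24% ever lose that much. The means appear to recover while the per-patient burden does not. This shows attrition only, because the example contains no unscheduled visits.

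**5. Off-schedule rule, assumed inputs.** In cycle 1 a share q has a dip of d% starting uniformly on day 7 to 21 and lasting L days. Other change has SD 2%. A weight is assumed to be taken at an unscheduled visit during every dip. A dip is still present at day 28 with probability 0 (L = 7), 0.5 (L = 14) or 1 (L = 28). The chance of a value at or below −5% is Φ(−2.5) = 0.0062 without a dip and Φ(1.5) = 0.9332 with an 8% dip. For q = 15% and d = 8:

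| Dip length | Day-28 mean | At least 5% loss, day 28 only |
|---|---|---|
| 7 days | 0.0% | 0.6% |
| 14 days | −8 × 0.075 = −0.6% | 0.075 × 0.9332 + 0.925 × 0.0062 = 7.6% |
| 28 days | −8 × 0.15 = −1.2% | 0.15 × 0.9332 + 0.85 × 0.0062 = 14.5% |

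With the unscheduled weights counted, the share is 14.5% in every row. Over q = 5 to 20% and d = 5 to 8%, it is about 3 to 19% with them. From day 28 alone it is 0.6% (7 days), 2 to 10% (14 days) or 3 to 19% (28 days, nothing lost).

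**The case against.** The case for leaving the plan alone is substantial, and most of it stands.

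- A reader might infer that the table shows change only and that every unscheduled value is discarded. Neither holds. Actual values are tabulated too, baseline is excepted, and the other values are left out of tables rather than deleted. The baseline exception follows from SAP 6.7, which takes the last non-missing value before first dose.
- A reader might infer that early stoppers vanish. They count in each period until they stop, and a scheduled EOT examination follows. In step 4, of the 16% who ever lose at least 5%, 13% are still on treatment at the scheduled week-8 visit, and the other 3% have an EOT examination. No loss in that example depends on an unscheduled value.
- SAP section 7 already makes N, minimum and maximum default statistics, so shrinking rows and the largest loss per row would usually be visible. A minimum is one patient, however, and does not say how many crossed a given level.
- Clinically relevant changes are recorded as AEs (Protocol 5.2.2.1) and tabulated per patient by highest grade (SAP 7.8.1), whichever visit they arise at. This route is sound but depends on investigator judgement and does not summarise the measurements.
- At unscheduled visits the protocol asks at a minimum for AE and dispensing entries (4.1.4.1, 6.1.3). Weights from those visits may not be in the eCRF, so a change to the SAP alone may recover little.
- Protocol 7.3.3 does not promise worst values, thresholds or unscheduled data, so the exclusion rule does not contradict it. Only the missing place for EOT values falls short of it.

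**Conclusion.** The point holds in a limited form and is minor. Three gaps in SAP 7.8.3 are established from the text: no stated place for EOT values, no per-patient worst or last value, and no display of post-baseline off-schedule values. Together they allow the tables to understate weight and vital-sign change.

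That they will do so, and by how much, is not established. The results in steps 4 and 5 rest on assumed shares, depths, durations and stopping times, and on PFS as a stand-in for time on treatment. The off-schedule effect disappears if losses last about four weeks, and it also needs weights to have been recorded at those visits. The stronger reading, that the plan biases the trial's safety conclusion, is not supported: the primary endpoint (patients with SAEs) and the AE tables do not use these data.

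**What to change.** In SAP 7.8.3, keep the 4-week table and state where EOT values go, for example in a row of their own.

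Add one table on the treated set giving each patient's worst and last on-treatment change from baseline. Use all recorded values from first dose to 28 days after last dose, which is the on-treatment analysis period of SAP 6.1: scheduled, EOT and any unscheduled values in the eCRF. For weight, give n (%) of treated patients in pre-set loss categories, for example at least 5%, 10% and 20%. For systolic pressure and pulse, give the lowest and highest values. The weight categories are for reporting only, are not taken from the documents and imply no treatment rule.

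The cost is SAP wording and one table. Worst-value summaries pick up measurement noise and will look slightly less favourable. Recovery of unscheduled values may be partial, so the table should say how many were available.

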#### **7.8.4 ECG**

Only the date of the tracing is collected if this is done per site standard of care. Abnormalities will be recorded with Baseline Conditions or Adverse Events as appropriate.

#### **7.8.5 Others**

Not applicable.

## **9. ADDITIONAL SECTIONS**

### **9.2 PROGRAMMING CODE FOR TIME TO EVENT ENDPOINTS**

For Kaplan-Meier estimates the following SAS code will be used:

```
proc lifetest data=<DATA> method=KM;  
time <ENDPOINT>*<CENSORED FLAG>(1);  
  
run;
```

Where:

DATA – name of the input dataset.

ENDPOINT – is the time variable (i.e. TTSP,

CENSORED FLAG – is the binary variable with value 1 denoting a censored observation and value 0 (zero) indicating the observation that was not censored (so the event had occurred)

## 10. HISTORY TABLE

Table 10: 1 History table

Version	Date (DD-MMM-YY)	Author	Sections changed	Brief description of change
Final	26-NOV-15		None	This is the final TSAP without any modification.
Revised	28-MAR-17		5.3, 6.1, 6.7, 7.5.2, 7.6, 9.1	
and
 
Revised the definition of study period in section 6.1;            Changed the follow-up visit window (section 6.7) to be consistent with the flow chart in CTP;            Revised the censoring rules for TTSP in section 7.5.2;
 
and

